14. PROVISIONS TO MONITOR THE DATA TO ENSURE THE SAFETY OF SUBJECTS*

The proposed study involves no more than minimal risk to participants. Therefore, we believe that an intensive data and safety monitoring plan is not needed. However, we will take steps to ensure the integrity of the data and to detect any adverse effects of the study on participants.

See also #27 Provisions to Protect the Privacy Interests of Subjects.

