“After the first minute, tell the patient the following (in even tones): “You are doing well. You have 5 minutes to go.” When the timer shows 4 minutes remaining, tell the patient the following: “Keep up the good work. You have 4 minutes to go.” When the timer shows 3 minutes remaining, tell the patient the following: “You are doing well. You are halfway done.” When the timer shows 2 minutes remaining, tell the patient the following: “Keep up the good work. You have only 2 minutes left.” When the timer shows only 1 minute remaining, tell the patient: “You are doing well. You have only 1 minute to go.” Do not use other words of encouragement (or body language to speed up). If the patient stops walking during the test and needs a rest, say this: “You can lean against the wall if you would like; then continue walking whenever you feel able.” Do not stop the timer. If the patient stops before the 6 minutes are up and refuses to continue (or you decide that they should not continue), wheel the chair over for the patient to sit on, discontinue the walk, and note on the worksheet the distance, the time stopped, and the reason for stopping prematurely. When the timer is 15 seconds from completion, say this: “In a moment I’m going to tell you to stop. When I do, just stop right where you are and I will come to you.” When the timer rings (or buzzes), say this: “Stop!” Walk over to the patient. Consider taking the chair if they look exhausted. Mark the spot where they stopped.”

INVESTIGATOR STUDY PLAN - REQUIRED

Randomization: we will randomize patients in a 1:1 fashion into intervention and control groups using a prespecified table generated by our study statistician. More specifically we will use REDCap software to assign a study arm assignment using randomly permuted blocks of sizes 4 and 6.

Intervention patients: intervention patients will receive a walking prescription weekly calls from a study staff member as described below

Walking prescription: A study staff member in consultation with study physician (PI or co-I) will then provide the initial walking prescription based on the participants' baseline performance on the 6MWD following a published example^{12,13} and will focus the participant on walking at a moderate intensity (level of approximately 3 on the modified Borg Perceived Exertional Scale;¹⁴ laminated Borg scales will be distributed to participants).

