Participants may walk steps over the course of a day or in one session. The initial walking prescription will also provide instructions to the participant to increase his/her number of steps each week by 10 to 20%.

A research staff member will then orient the participant to the pedometer

Weekly calls: During the interim between the day of consultation until the day of surgery, a study staff member will make weekly calls to each patient. The calls will provide participants an opportunity to report any symptoms which could warrant stopping the walking regimen and/or seeking urgent medical attention. In addition, we will train the study staff member to troubleshoot any problems setting step count targets or other problems with the pedometer. In cases in which the pedometer fails, we will budget to have additional pedometers available to mail to the patient.

Activity log: we will ask participants to log all of their physical activities-date, activity type, number of minutes. We will submit a copy of the activity log to the irb for approval prior to recruiting randomized participants to complete it.

Control subjects: a study staff member will provide general walking advice with typical warnings about when to stop (e.g., chest pain, breathing difficulty, or fall). Control subjects will receive no other intervention. We will also ask control subjects to log their physical activities.

Preoperative assessment: On the day of preoperative testing, which will usually occur three to five weeks after the baseline measurement, a research staff member or other project staff member will collect the pedometer and record the repeat physical status assessments (6MWD and SPPB). On the day of surgery, we may also place a research grade monitor on patients so as to track their steps while in the hospital.

Hospital period assessment: By the day of discharge, we will collect the research grade monitors and repeat our physical status measurements.

INVESTIGATOR STUDY PLAN - REQUIRED

In order to test the above procedures in the randomized individuals, we will enroll up to 15 patients as test patients. All these patients will undergo screening, baseline assessment/interview, follow-up assessment on day of preoperative testing, in-hospital step tracking and Hospital period assessment.

30 day assessment: Approximately 30 days from day of surgery, at office of surgery clinic, we will repeat our physical status measurements

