Interim Analyses: Given the possibility that our walking intervention does not improve our physical status measures, we will perform the Aim 1 analysis after recruitment of each batch of 10 patients. More specifically, we will assess the average and median change against the MCID for each of the five measures. If we have not achieved the MCID for any of the measures after any one batch, we will work with our advisors, particularly [name], to revise our intervention (e.g. intensifying the walking regimen) with the goal of improving physical status more than the MCID of one or more measures by the time of the next interim analysis.

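### During home walking, harm is picked up only through weekly intervention-arm calls that nobody is assigned to review, and the batch-of-10 rule can lead to harder walking with no safety information required

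*Combined protocol and SAP*

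**What the plan says.** Section 14 considers the study minimal risk and an intensive monitoring plan unnecessary, then adds that "we will take steps to ensure the integrity of the data and to detect any adverse effects of the study on participants". It does not say what those steps are, and its only cross-reference is to the privacy section (27).

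Section 11 states that "intervention patients will receive a walking prescription weekly calls from a study staff member as described below". The calls are timed as "During the interim between the day of consultation until the day of surgery", and "The calls will provide participants an opportunity to report any symptoms which could warrant stopping the walking regimen" or seeking urgent care. Controls get general walking advice with stop warnings and an activity log, and are to have nothing further. The log, kept by both arms, covers date, type and minutes of activity. The preoperative visit is described as taking back the pedometer and repeating the six-minute walk and the physical performance battery.

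On dose, section 11 reads "A study staff member in consultation with study physician (PI or co-I) will then provide the initial walking prescription". Participants are told to "increase his/her number of steps each week by 10 to 20" percent, at a moderate effort of about 3 on the modified Borg scale.

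In section 13, Interim Analyses, mean and median change on five physical measures is compared with the MCID after every ten recruits. The rule continues: "If we have not achieved the MCID for any of the measures after any one batch", the team will work with its advisers "to revise our intervention (e.g. intensifying the walking regimen").

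**The concern.** Section 16 itself names falls, chest pain and shortness of breath as risks. The participants are frail, and sections 6 and 18 also admit cognitively impaired patients, promising them close monitoring without saying how that works at home. The clinician cover in section 16 is on the premises, so it does not reach the home, where the prescribed walking takes place.

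Two things are at stake. First, walking can be made harder for later patients without anyone having to look at what earlier patients reported on their calls. Second, because only one arm is asked, falls or chest pain among prescribed walkers cannot be set against the background rate in similar patients awaiting surgery. A few falls in the intervention arm could then be neither attributed to the regimen nor dismissed. This matters because the study is meant to prepare for a larger trial.

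**Working it through.** The plan gives no adverse event rate and no safety calculation to reproduce. The check is mainly a reading of the text, with some arithmetic for scale.

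**Routes to detect harm, by period**
- *Entry:* section 6 excludes recent falls, angina at rest or on minimal exertion, high heart rate or blood pressure, and patients who do not walk independently. This lowers risk at the start but detects nothing afterwards.
- *Baseline to preoperative visit, intervention arm:* weekly calls inviting symptom reports. No form, compiler or reviewer is named.
- *Baseline to preoperative visit, control arm:* stop warnings at the outset and an activity log with no symptom or fall field described.
- *Preoperative visit, both arms:* physical measures only, as described.
- *After surgery:* 30-day outcomes by chart review (section 13, Aim 3) and, at the six-month contact, complications since surgery (section 11). Neither looks back at the walking period.

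The calls paragraph speaks of each patient, which could be read as both arms. The sentence assigning the calls to intervention patients, and the statement that controls get nothing else, point to one arm.

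**Scheduled chances to report symptoms before the preoperative visit**
The visit usually falls 3 to 5 weeks after baseline (section 11). At one call a week that is about 3 to 5 per intervention patient and 0 per control.

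**Growth of the unrevised regimen**
With a weekly rise of 10% to 20%, the target in week k is 1.1^(k−1) to 1.2^(k−1) times the starting target.
- Week 3: 1.1² = 1.21 to 1.2² = 1.44.
- Week 5: 1.1⁴ = 1.46 to 1.2⁴ = 2.07.

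An intensified regimen would add to this.

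**Upper bound on revisions**
The documents give both 200 patients (section 24; section 13, Aim 2) and 400 (sections 4, 10 and 25). Assume that all of them count toward batches and that the rule is triggered at every review. The last review has no later patients to affect.
- 200/10 − 1 = 19.
- 400/10 − 1 = 39.

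The documents give no basis for how often the rule would be triggered, so these are ceilings.

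**Precision of a by-arm count, if one were collected**
Half-width of the 95% interval for a risk difference = 1.96 × √(2p(1−p)/n), with p = 10% in each arm (an assumption).
- n = 100 per arm: 1.96 × √(0.18/100) = 8.3 points.
- n = 200 per arm: 1.96 × √(0.18/200) = 5.9 points.

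**The case against.** The strongest reply is that the plan already has proportionate cover for a minimal-risk activity. The weekly calls sit in the arm that receives the prescription and serve to stop the regimen or direct a patient to urgent care. Exclusions remove those most likely to be harmed, and the Borg target limits effort whatever the step count. A physician is consulted on each initial prescription and the principal investigator oversees prescriptions (section 23), so an intensified regimen for new patients would pass through a clinician. Section 11 leaves scripts and forms to be written and allows no data collection until the IRB has approved them, so symptom items may yet appear. The plan proposes no by-arm comparison of preoperative symptoms, and such counts would be imprecise and affected by unequal recall.

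Much of this stands. A reader might infer that the plan has no procedure for detecting harm at home; the weekly calls show otherwise. A reader might also infer that a missed MCID makes walking harder automatically; the text requires work with advisers and offers intensifying only as an example. Nor should 19 or 39 be read as an expected number of revisions. The stated goal is to pass the MCID on one or more measures, so the natural trigger is missing it on all five.

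What the reply does not supply is a link between call reports and the decision to intensify. The advisers are given an efficacy goal and no safety information. Physician input concerns the individual prescription; it is not tied to the batch rule and requires no look at accumulated reports. IRB review of forms allows symptom items to be added, but the text does not call for them.

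**Conclusion.** The point holds in a limited form. In the prescribed-walking arm, harm can be reported, but the text does not say who gathers or reads the reports. In controls, nothing equivalent is asked before surgery. The batch rule can lead to a harder regimen on efficacy results alone. Existing safeguards reduce the risk at entry and for the individual patient; they do not provide a review across patients.

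The conclusion rests on reading the calls as intervention-only, which the text favours but does not put beyond doubt, and on the forms not adding what the text omits. It depends on no assumed event rate. The documents do not support a claim that patients are being harmed, that a data monitoring committee is needed, or that a planned safety comparison is invalid. This should be changed because the remedy is cheap and the participants are frail; it does not undermine the physical status analyses.

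**What to change.** 1. At the preoperative visit already scheduled for both arms, ask the same short list: falls, chest pain, breathlessness and unplanned care since baseline. Report the counts by arm at the end of the study, descriptively, with the number in each arm who missed the visit and a note that weekly calls may sharpen recall in the intervention arm.
2. Before any intensification under the batch rule, have the study physician (PI or co-I) review and sign off a cumulative intervention-arm listing of falls, symptoms and regimen stops, drawn from the calls and visits. Include patients not yet at the visit, those who withdrew and those whose surgery was cancelled. No by-arm table, test or threshold is needed at these reviews.
3. State both steps in section 14, so that its promise points to a procedure.

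The cost is about two minutes per patient at an existing visit and one listing per proposed revision. No calls are added for controls, so the contrast between arms is preserved. The limits are the imprecision computed above and unequal recall, which a common question list reduces but does not remove.

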15. WITHDRAWAL OF SUBJECTS WITHOUT THEIR CONSENT*

We do not anticipate the need to withdraw patients unless it is at their request. However, we will remove patients who appear unduly distressed during the research interview.

16. RISKS TO SUBJECTS*

Potential Risks

INVESTIGATOR STUDY PLAN - REQUIRED

The proposed study poses minimal risks to the participants. There is a slight risk that research records (interview forms, interview notes, audio-recordings, transcripts, and electronic data) might be obtained by persons not authorized to do so. There is a slight risk that research data files might be compromised, and obtained or viewed by unauthorized persons. There is also a risk that the patient may feel uncomfortable answering some of the questions in the interviews. We will inform all patients during the informed consent process that they do not have to answer any questions that they do not want to. There is also a risk that the patient may fall. We screen patients initially based on prior falls to minimize this risk. In addition, there is screening for cognitive impairment for patients who may not fully appreciate risks of walking. The same screening process protects patients against development of chest pain or shortness of breath. We exclude patients with existing angina in such that small amount of walking or being at rest (i.e. class III or IV angina). We also have a physician or nurse on the premises at all times responsible for the patient if he or she were to develop shortness of breath, chest pain, or fall.

See also #14 Provisions to Monitor the Data to Ensure the Safety of Subjects, and #27 Provisions to Protect the Privacy Interests of Subjects.

17. POTENTIAL DIRECT BENEFITS TO SUBJECTS*

The walking intervention has the potential to decrease adverse post-surgical outcomes for patients involved in our study, but cannot be guaranteed.

18. VULNERABLE POPULATIONS*

Adults unable to consent (adults lacking capacity)

Given the topic of study and the inclusion/exclusion criteria, it is possible that potential participants with impaired decisional competency will be identified for this study. However, this study has anticipated direct benefits to subjects, and we will therefore enroll cognitively impaired patients. We will implement consent procedures consistent with those recommended for patients with cognitive impairment. This includes reviewing consent with a legally authorized representative and close monitoring of patients. If patients appear unduly distressed, they will be withdrawn from the study. Please see section # 30. Consent Process for additional details.

Individuals who are not yet adults (infants, children, teenagers)

This study excludes anyone who is less than 65 years old; no children will be included in this study.

Pregnant women

Pregnant women will not be included.

Prisoners

Prisoners will not be included in the study.

Non-English speaking subjects

Patients speaking a language for which the UMass IRB does not have a short form consents available will not be included. For non-English speaking patients, we will utilize an interpretive

INVESTIGATOR STUDY PLAN - REQUIRED

service referred to us by UMass Memorial Interpretive Services. The interpretive service will not be given any information about the patients we enroll. They are only notified of the department from which we are calling from.

We will use the telephone interpretive services or a family member who is conversant in English and the language understood by the subject to conduct the interview. We will use the short forms provided by the UMass IRB. We will have the interpreter or family member act as the witness. If the interpreter is the only witness, we will send the consent form for his/her signature and keep a copy of the version signed by the interpreter. Because the involvement of each patient does not extend beyond one interview study session, we will not reassess consent with the research participant.

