6. INCLUSION AND EXCLUSION CRITERIA*

Inclusion criteria for screening - We will enroll participants age 50 and older undergoing any abdominal or thoracic surgery.

Inclusion criteria for randomized controlled trial - We will enroll participants age 50 and older undergoing any abdominal or thoracic surgery.

Exclusions for screening – non-adults, prisoners, Non-English language speaker for whom short form consent is not available.

Exclusions for randomized controlled trial - The exclusions we will apply pertain mainly to the measurement of 6MWD – (1) unstable angina or stable angina with minimal exertion or at rest (2) visual impairment such that walking impairs safety (3) fall within previous three months, (4) resting heart rate of more than 120, a systolic blood pressure of more than 180 mm Hg, or a diastolic blood pressure of more than 100 mm Hg (5) patient who does not walk independently (e.g. wheel chair; cane walking is ok)

Individuals who are not yet adults (infants, children, teenagers)

This study excludes anyone who is less than 50 years old; no children will be included in this study.

Pregnant women

Pregnant women will not be included.

Prisoners

Prisoners will not be included in the study.

Non-English language speaking subjects

INVESTIGATOR STUDY PLAN - REQUIRED

Non-English language speaking subjects for which an IRB approved short form is available will be included; patients speaking a language for which the UMass IRB does not have a short form consents available will not be included.

Adults unable to consent (adults lacking capacity)

Adults who are deemed cognitively impaired or unable to consent will be included; given the topic of study and the inclusion/exclusion criteria, it is possible that potential participants with impaired decisional competency will be identified for this study. If substantial cognitive impairment is indicated through the use of the MiniCog test, we will implement consent procedures consistent with those recommended for patients with cognitive impairment. This includes reviewing consent with a legally authorized representative and close monitoring of patients. If patients appear unduly distressed, they will be withdrawn from the study. Please see section # 30. Consent Process for additional details.

*See also section #18.

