9. STUDY TIMELINES*

The overall study timeline is two years from start of recruitment. The first year will focus on preparation (training on frailty measurement, scripting interviews, and testing the questions we ask) and recruitment of study subjects. Individual subjects will be actively involved for 30 minutes during their first appointment (not including time spent in clinic appointment), approximately 15 minutes during the day of their surgery, and potentially approximately ten additional minutes on their day of discharge from the hospital, though patient data collection will continue for up to one year after the day of surgery.

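### Sections 18 and 30 waive reassessment of consent because involvement is a single session, but the protocol's own schedule gives every participant at least two study contacts

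*Combined protocol and SAP*

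**What the plan says.** Section 6 makes language a matter of available paperwork: "Non-English language speaking subjects for which an IRB approved short form is available will be included". Sections 18 and 30 then describe how these patients are handled. Both open with a general statement that an interpretive service will be used. They go on to provide for telephone interpretation or "a family member who is conversant in English and the language understood by the subject to conduct the interview", and add: "We will have the interpreter or family member act as the witness". In both sections the paragraph ends with the same sentence: "Because the involvement of each patient does not extend beyond one interview study session, we will not reassess consent with the research participant".

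Elsewhere the protocol describes longer involvement. Section 9 says "Individual subjects will be actively involved for 30 minutes during their first appointment", then adds time on the day of surgery and possibly at discharge, "though patient data collection will continue for up to one year after the day of surgery". Section 11 sets out a baseline assessment, a preoperative assessment, a hospital-period assessment, a 30-day clinic assessment and a six-month contact. It also says that "intervention patients will receive a walking prescription weekly calls from a study staff member as described below", and of those calls: "During the interim between the day of consultation until the day of surgery, a study staff member will make weekly calls to each patient".

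**The concern.** The one-session statement is the only reason the protocol gives for a substantive decision about consent. If the reason is wrong, the decision has no stated basis. It also stands in the two sections that staff would consult on how to consent a non-English speaker.

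The second issue is language support after the first visit. Section 11 gives the weekly calls a safety purpose: they are where a patient walking at home can report symptoms that bear on stopping or on seeking urgent care. They are the only scheduled symptom check that Section 11 describes for that period, and Section 14 says an intensive safety monitoring plan is not needed. The 6MWD, repeated at several assessments, is run on a fixed spoken script with prompts at each minute. Both procedures depend on the patient understanding the staff member, and the protocol does not say how that is secured for patients admitted under the language criterion.

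**Working it through.** The protocol gives no figure to reproduce. The check sets the one-session premise against the contact schedule, by category of participant.

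**Inputs**
- Premise (Sections 18 and 30): 1 session per patient.
- Screened but not randomized (Section 11): no further participation except a six-month interview.
- Randomized patients (Section 11): baseline; preoperative testing, usually three to five weeks later; hospital period, by discharge; 30 days; six months, with attempts made in months 7 and 8.
- Weekly calls (Section 11): listed under the intervention arm. The later phrase about calling each patient is read here as each intervention patient, because controls are said to receive no intervention beyond general walking advice.
- Test patients who are not randomized (Section 11, up to 15): baseline, preoperative follow-up, in-hospital step tracking and hospital assessment.

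**Count of planned contacts**
- Screened only: screening + six-month interview = 1 + 1 = 2.
- Randomized control: baseline + preoperative + hospital + 30-day + six-month = 5.
- Randomized intervention: 5 + weekly calls. At one call per week over three to five weeks, 5 + 3 = 8 to 5 + 5 = 10. Calls run to the day of surgery rather than to preoperative testing, so the number could be higher.
- Test patients: baseline + preoperative + hospital = at least 3.

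The smallest count is 2, so no category fits the premise of 1. Section 9 alone is enough to show this: it lists active involvement at the first appointment and again on the day of surgery.

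**Language support, contact by contact**
- Consent: covered (short form; interpreter or family member as witness).
- The interview: covered (telephone interpreter or family member).
- Weekly calls, scripted 6MWD instructions and repeat physical assessments: not mentioned in the language provisions.
- Six-month contact: not mentioned by name, though Section 11 calls it an interview, so the existing wording could be read to include it.

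**The case against.** The strongest reply is that this is a misfitting sentence with little behind it. Enrolment of non-English speakers does not depend on it. The interpreter paragraphs open in general terms. Withdrawal at the patient's request is recognised in Section 15, and Section 30 refers to a consent SOP, not included in the documents, that may cover continuing consent. Nothing here alters an estimand, the sample size or an error rate.

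Much of that stands, and it limits what can be claimed. A reader might infer several stronger things that the documents do not support:
- *That non-English speakers are admitted because involvement is a single session.* Section 6 ties admission to a short form being available. The one-session sentence justifies only the decision not to reassess consent.
- *That interpretation is excluded after the first interview.* The general opening sentence prevents that reading. Support at later contacts is unspecified, not ruled out.
- *That 6MWD change scores are biased in these patients.* This would need an interpreted baseline and uninterpreted repeat tests, and no section says so.
- *That the waiver reaches patients enrolled through a surrogate.* The words refer to each patient, but the sentence closes the paragraphs on interpreters. Adults lacking capacity have separate provisions in Sections 6, 18 and 30.
- *That a particular number of patients is affected.* The documents give no share of non-English speakers.

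The reply does not rescue the sentence itself. Reading it narrowly, as referring to one interview with other visits not counted, fails on two grounds: it speaks of the patient's involvement as a whole, and Section 11 describes a later interview at six months.

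**Conclusion.** The point holds as an internal contradiction with a practical consequence. The stated reason for not reassessing consent is false for every category of participant: 2 contacts for screened-only patients, at least 3 for test patients, 5 for controls and about 8 to 10 for intervention patients, against the 1 assumed. The intervention figure assumes one call per week over three to five weeks; the other counts are read directly from Section 11. The contradiction does not depend on that assumption.

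On language support the finding is a gap in specification. It matters most for the weekly calls, because of their safety purpose, and it concerns the intervention arm only. It should be corrected because the current text gives staff a wrong basis for a consent decision and the remedy is small. It does not show that any patient would go without an interpreter or that any outcome is distorted.

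**What to change.** - Delete the one-session sentence in both Section 18 and Section 30, and reconcile those sections with the schedule in Sections 9 and 11.
- Replace it with a statement that staff will briefly confirm, verbally, that the patient is willing to continue at later study contacts. Formal re-consent at each named visit is not needed to resolve the contradiction.
- State that the telephone interpreter service already named is used at all study contacts, including the weekly symptom calls and the scripted 6MWD instructions at baseline and at every repeat test.

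The cost is a short amendment to two sections, a brief verbal check at contacts that already take place, and modest extra use of the interpreter service. No new visits or staff are required.
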